#### **4.5.2 Handling of Subject Withdrawals or Subject Discontinuation of the Investigational Device**

Subjects withdrawn early due to an AE will be followed until medically stable or resolution of the AE.

If withdrawal from the study is requested by the subject, prior to BTM integration (i.e. **before Day 7** post-implantation), the BTM device can be removed and the wound bed closed by the application of an autologous SSG. However, **≥ Day 7** the BTM can be removed, but it is **not recommended**, as integration will likely have occurred to a point such that BTM removal would result in damage to the subject's burn wound. In either case, no data or BTM -related follow-up will be imposed. Physicians are expected to follow subjects according to their institution's standard of care. Investigational Device Exemption (IDE) regulations require investigators to maintain each subject's case history and exposure to the device.

All consented subjects who have been implanted with BTM, even in the event of device failure, will have all lesions followed up as a part of the study until completion or if/when withdrawal from the study is requested by the subject.

If subjects do not complete 3 months follow up **post SSG** implantation for any reason, they will be replaced with further subjects that meet the inclusion/exclusion criteria, to

ensure that the final cohort is (a minimum of) 10 subjects.

In case of withdrawal, the Investigator will promptly inform the Institutional Review Board (IRB) within 5 working days and will provide the reason(s) for the withdrawal. All applicable source documentation will be collected to confirm resolution.

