### **6.3 BTM 'Take' Visit #3 (Every 3 - 5 days from day of BTM application until SSG)**

- Perform full physical examination with recording of vital signs results.
- Review concomitant medication(s) history.
- Assessment of any infection (BTM or non-BTM related) (A clinical diagnosis supported by confirmatory laboratory findings).
- Assessment of adverse events.
- Assessment of BTM integration and examination for signs of incomplete spontaneous delamination.

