- An assessment of the %SSG 'take' rate will be measured by the amount of applied skin graft which remains viable ('takes') expressed as a percentage of the total amount of SSG applied at 7 -10 days after application of the SSG (Section 11.3).
- An assessment of the quality of the wound will be measured using active Range of Motion (ROM) of affected joints when possible and severity of joint contracture (Appendix 2). The details regarding the assessment of the grading for mild, moderate and severe contractions are also included in Appendix 2.
- An assessment of % wound closure for each BTM-treated burn wound.
- Scar appearance/quality will be assessed using the modified Vancouver Scar Scale (mVSS) (Appendix 2).
- Pruritus incidence and severity will be assessed by the Numerical Rating Scale (NRS) (Appendix 2). [The eCRF will also capture duration, NRS scale (intensity), disability, and distribution on the body.]
- Physicians will be surveyed to assess Ease of Use. The eCRF will capture ease of BTM application, delamination, time, and overall impressions.
- Subjects will be called monthly to collect adverse events and changes to medications and any non-trial visits with a physician regarding their burn or burn treatment (specify physician type: general practitioner, physical therapist, other: specify).

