## 8 ASSESSMENT OF SAFETY

Subjects will be monitored throughout the clinical trial for adverse events/effects. Subjects will be instructed on the need to inform the Investigator and/or clinical trial staff of any AEs that may occur at any time during the clinical trial.

Adverse events considered related to the investigational device (ID), as judged by a medically qualified Investigator or PolyNovo, will be followed either until resolution or the event is considered medically stable.

It will be left to the Investigator's clinical judgment to decide whether or not an AE is of sufficient severity to require the participant's removal from treatment, prior to Day 7 after BTM implantation. A participant may also voluntarily withdraw from treatment until Day 7 after BTM implantation without giving a reason. In either event, a Termination visit assessment will be performed. In the event of AE termination by the Investigator, the subject will be given appropriate medical care until symptoms cease, or until the condition becomes stable.

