## **8.2 Time Period and Frequency for Event Assessment and Follow-Up**

Adverse events, SAEs will be recorded in the data collection system throughout the trial and the subject followed until resolution or they are considered medically stable.

The PI will record all adverse events with start dates occurring any time after informed consent is obtained until 7 days (for AEs) or 30 days (for SAEs) after the last day of trial participation. At each visit, the Investigator will inquire about the occurrence of AE/SAEs since the last visit. Events will be followed for outcome information until resolution or stabilization.

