2.3. Overall Study Design and Plan

This is a multicenter, single arm, open-label study to allow a preliminary assessment of the safety and effectiveness of BTM device. Patients with 10-70% TBSA burns will have BTM devices implanted in areas with deep partial or full thickness burns to treat at least 5% and no more than 50%TBSA.

This trial aims to recruit a minimum of ten subjects and up to 15 subjects suffering deep-dermal or full thickness burn injuries to between 10% and 70% TBSA and who are able to provide informed consent, or have a legal representative who is able to make medical decisions on behalf of the subject.

The study will consist of approximately a 1-2 day screening period, a 2 month treatment period, and a 12 months follow-up period. The screening period will start from the day of signing the Informed Consent Form until Day 0 of treatment within 7 days. The treatment period will last approximately 2 months starting from admission to hospital through to the end of graft 'take'. The follow-up period will start from the day after the end of graft take date.

There is no restriction on administration to the subject of their usual medication, or such pharmaceutical treatments felt necessary by the Investigator such as antibiotics or topical aqueous only antimicrobial solutions.

Subjects will be monitored throughout the clinical trial for adverse events/effects. It will be left to the Investigator's clinical judgment to decide whether or not an AE is of sufficient severity to require the participant's removal from the trial, prior to Day 7 after BTM implantation. A participant may also voluntarily withdraw from follow-up treatment after BTM implantation without giving a reason. In either event, a Termination visit assessment will be performed. In the event of AE termination by the Investigator, the subject will be given appropriate medical care until symptoms cease, or until the condition becomes stable.

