8.1. Adverse Events

An AE can be any unfavorable and unintended sign (including an abnormal laboratory finding, for example), symptom, or disease temporally associated with the use of an investigational product, whether or not considered related to the product. All AEs encountered during the study will be reported in detail in the CRF, starting at the time of the first screening/eligibility assessment and ending at the end of the study for each subject. Pre-existing conditions that worsen during a study are to be reported as AEs. Clinically significant changes in physical examination, standard of care laboratory safety tests, and vital signs will also be defined as AEs and recorded appropriately. All AEs will be coded using the MedDRA Dictionary (MedDRA, Version 18.1 or higher).

A study-specific subset of AE events called Unanticipated Adverse Device Effect (UADE) will be introduced to the safety analysis of this study. UADE is defined as “any serious adverse effect on health or safety or any life-threatening problem or death caused by, or associated with, a device, if that effect, problem, or death, was not previously identified in a nature, severity, or degree of incidence in the investigational plan or application (including a supplementary plan or application), or any other unanticipated serious problem associated with a device that relates to the rights, safety, or welfare of subjects” (21 CFR 812.3). The UADE will be identified by the Principal Investigator (PI) on site and reported in the CRFs.

Imputation for missing AE onset dates can be found in Appendix 13.3.

An overview summary of the number and percentage of subjects with any AE, SAE, AE related to study device, AE leading to early termination, and AE leading to death will be provided with ITT population. A repeated analysis will be conducted for the subset of UADEs.

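### Protocol 4.5.2 lets a site skip the Early Termination visit when an implanted subject asks to leave, and is not reconciled with Protocol 8 or SAP 2.3, which say a termination visit is done

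*Protocol*

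**What the plan says.** Four places bear on what happens when an implanted subject asks to leave.

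- **Protocol 4.5.2** treats withdrawal from the study at the subject's request in two cases, before Day 7 and from Day 7 on. It then says: "In either case, no data or BTM -related follow-up will be imposed". Lesion follow-up for implanted subjects runs "until completion or if/when withdrawal from the study is requested by the subject". Care after that follows the institution's own standard.
- **Protocol 8** covers removal for an AE and voluntary withdrawal from treatment. The second is allowed "until Day 7 after BTM implantation without giving a reason. In either event, a Termination visit assessment will be performed".
- **SAP 2.3** repeats this without the day limit: a participant may withdraw "from follow-up treatment after BTM implantation without giving a reason. In either event, a Termination visit assessment will be performed".
- **Protocol 6.8** lists the Early Termination assessments, including physical examination, infection, joint contracture, wound closure, scar, pruritus, AEs and photographs. It does not say which subjects get them. The visit also appears in Protocol 7.1 (weight), 7.4.2 (photographs), Appendix 1 and SAP 12.1, none of which has a Day 7 limit.

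Protocol 8.2 sets the AE recording window for everyone: "until 7 days (for AEs) or 30 days (for SAEs) after the last day of trial participation". It does not mention withdrawn subjects. SAP 8.1 describes AE reporting as "starting at the time of the first screening/eligibility assessment and ending at the end of the study for each subject" and does not mention the 7-day and 30-day windows.

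**The concern.** A site that reads 4.5.2 literally has grounds for closing the record on the day of the request. A site that reads Section 8 or SAP 2.3 carries out a full exit assessment. Both are following the plan.

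The question matters most from Day 7 on. Removal of the device is then advised against, so the subject will usually leave with the implant in place. SAP 3.3.2 keeps every treated subject in the ITT population, and SAP 3 takes the denominator for percentages from that population. In an incidence table, an event that nobody asked about looks the same as no event. The incidence and type of AEs is one of the three primary endpoints, and the cohort is only 10 to 15 subjects.

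**Working it through.** The plan gives no figure to reproduce on this point. The check is a comparison of texts followed by simple arithmetic.

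**Step 1. Which text calls for the visit, by time of a subject-requested withdrawal.**

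| Time of withdrawal | Protocol 4.5.2 | Protocol 8 | SAP 2.3 | Protocol 6.8 and schedules |
|---|---|---|---|---|
| Before Day 7 | nothing imposed | visit performed | visit performed | visit defined, no day limit |
| Day 7 or later | nothing imposed | silent | visit performed | visit defined, no day limit |

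The direct clash inside the Protocol is confined to the period before Day 7. After that, 4.5.2 stands against SAP 2.3 and against a scheduled visit whose recipients are not stated.

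**Step 2. AE information at risk for one withdrawal.** The longest time since the last review follows from the contact schedule:

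- Up to SSG: reviews take place "Every 3 - 5 days from day of BTM application until SSG", so at most 5 days.
- SSG to Visit 5: Visit 5 falls 7 to 10 days after SSG, so at most 10 days.
- After Visit 5: visits or calls are about monthly ("Subjects will be called monthly to collect adverse events and changes to medications", Protocol 7.1), so about 30 days, taking one month as 30 days.

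This is what the exit visit itself would recover. If 4.5.2 is also read as cancelling the 8.2 windows, add 7 days for AEs and 30 days for SAEs:

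| Period | Since last review | With AE window | With SAE window |
|---|---|---|---|
| Up to SSG | 5 days | 5 + 7 = 12 days | 5 + 30 = 35 days |
| SSG to Visit 5 | 10 days | 10 + 7 = 17 days | 10 + 30 = 40 days |
| After Visit 5 | about 30 days | 30 + 7 = 37 days | 30 + 30 = 60 days |

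All of these are ceilings. They assume that the subject leaves just before the next contact and that nothing is learned when the request is made.

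**Step 3. Effect on an AE table.** SAP 8.1.1 counts a subject once at each level. A missed event therefore changes a row only if that subject has no other event in it. The row is then too low by 1/N:

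- N = 15: 1/15 = 6.7 percentage points.
- N = 10: 1/10 = 10.0 percentage points.
- Subject left before 3 months post SSG and was replaced (Protocol 4.5.2): the final cohort of at least 10 plus the withdrawn subject gives N of at least 11, so at most 1/11 = 9.1 percentage points.

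The documents give no expected number of withdrawals, so an expected bias cannot be calculated.

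**The case against.** The strongest case on the other side is that the texts can be read together. The sentence in 4.5.2 may concern only contact after the subject has left, and a termination visit closes participation rather than following it. *Imposed* may mean no more than not compulsory. Withdrawal from treatment in Section 8 may be a different event from withdrawal from the study in 4.5.2. The visit is in 6.8 and both schedules, and its name suggests who should have it. Section 4.5.2 itself asks for source documentation to be collected on withdrawal. Section 8.2 makes no exception for withdrawn subjects.

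Much of this stands. It makes the likely intent clear, and it rules out three stronger conclusions that a reader might draw:

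- *That the Protocol forbids the exit visit, or contradicts itself at every time point.* It does neither. Section 4.5.2 declines to impose follow-up, and Section 8 stops at Day 7.
- *That 12 to 60 days of AE data are lost with each withdrawal.* The visit alone recovers the time since the last review. The larger figures need the further reading that 4.5.2 overrides 8.2, which no text states.
- *That the AE rates will be biased.* Subjects who leave because of an AE are followed until they are stable or recovered, the reason for withdrawal goes to the IRB, and standard care continues. Protocol 5.5 also expects the device to be inspected every three to four days until graft take, with subjects typically in hospital.

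What does not stand is that the matter is already settled. No section states any of the easing readings, and none tells sites to ask for the visit. Standard care is not trial data, and a reason for leaving is not an AE inquiry.

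**Conclusion.** The inconsistency is real, and its importance is minor to moderate. The plan probably means the Early Termination visit to be done, but 4.5.2 as written allows a site to omit it for a subject-requested withdrawal. The worst period for safety information (from Day 7, implant usually in place) is not the period of the direct Protocol clash (before Day 7), and this limits the point.

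Per withdrawal, the exposure is the time since the last review, plus the 8.2 windows only on the less natural reading. A missed event costs a table row about 7 to 10 percentage points, and only if it is the subject's sole event in that row. The result rests on the contact intervals in the schedule, a 30-day month, and an ITT set of 10 to 15. No endpoint is invalidated. The study is descriptive and tests no hypothesis. It is meant to inform a pivotal trial, however, so the exit rule is worth settling now.

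**What to change.** State one rule in Protocol 4.5.2 and 8, with matching text in SAP 2.3. Every BTM-implanted subject who withdraws, at any time, is asked to complete the Section 6.8 Early Termination assessments and one AE/SAE contact at about 30 days, which covers both windows in 8.2. The data are collected unless the subject declines. A cross-reference in 6.8 would make clear who gets the visit. A line in the SAP 4.1 disposition table counting those who declined is optional.

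The cost is a sentence in each of two Protocol sections and a matching edit in the SAP. For the subject, it is one exit visit that is already in the schedule and one call, either of which may be refused. Device management and the right to withdraw do not change.

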#### **4.6 Premature Termination or Suspension of Trial**

This trial may be suspended or prematurely terminated if there is sufficient reasonable cause. Written notification, documenting the reason for trial suspension or termination, will be provided by PolyNovo and agreed upon by the DSMB. If the trial is prematurely terminated or suspended, the Investigator is responsible for promptly informing subjects and the IRB with the reason(s) for the termination or suspension.

Circumstances that may warrant termination include, but are not limited to:

- Determination of unanticipated, significant, or unacceptable risk (e.g. serious adverse device effect) to subjects
- Insufficient adherence to protocol requirements
- Data that are not sufficiently complete and/or evaluable

Halting rules will be included in the DSMB Charter and Statistical Analysis Plan.

## 5 INVESTIGATIONAL PRODUCT

### 5.1 Medical Device Description

BTM is a fully synthetic biodegradable dressing that is composed of three layers.

- Dermal component: A 2 mm thick, white, open cell, degradable polyurethane foam (pore sizes of 100-600  $\mu\text{m}$ ) with a high degree of porosity (~94%) providing a scaffold for dermal tissue integration
- Epidermal component: A temporary bonding layer designed to adhere the sealing polyurethane film/membrane (65  $\mu\text{m}$  thick) to the dermal foam
- Membrane: A temporary 50  $\mu\text{m}$  thick, transparent, fenestrated, polyurethane sealing membrane designed to physiologically close the wound and limit evaporative water loss

BTM is indicated for primary dermal repair after excision of deep dermal and full thickness thermal burn injury in adults. Usually such definitive epidermal closure is provided by skin autograft. BTM is designed to be implanted into the newly created wound bed and stapled or sutured to the edge of the wound. The BTM provides a scaffold to facilitate dermal repair whilst keeping the wound physiologically 'closed to reduce wound contraction'. After integration, the **combined** bonding layer and sealing membrane is peeled off and discarded, leaving only the implanted foam layer to biodegrade. The timing of the de-lamination is at the discretion of the Investigator based on his/her clinical and surgical judgement. Past clinical experience has placed this de-lamination between Days 21–56, but can be extended beyond 56 days if required. The wound bed is refreshed (e.g. by dermabrasion) and finally closed with a thin SSG.

#### 5.1.1 Supply

All component parts of the BTM are manufactured, assembled packaged and pre-sterilized by PolyNovo Biomaterials Pty Ltd, Port Melbourne, Victoria, Australia. The facility is ISO 13485 compliant and audited to the requirements of 21 CFR Part 820. The investigational device will be supplied to the investigating sites through a product depot vendor.

The proposed device is intended to be supplied in various sizes, including 20 cm  $\times$  10 cm, and 20 cm  $\times$  40 cm. The devices supplied for this trial will be 20 cm  $\times$  40 cm. The dressings are single use, terminally sterilized devices (by gamma-irradiation at 25kGy) that are individually packed in a polymer pouch within an aluminized envelope for

moisture resistance. The packaging is designed to be opened in a surgical setting so as to preserve the sterility of the operating field.

### **5.1.2 Packaging and Labeling**

The BTM device is dry-packed in multilayered, hydration-proof packaging and labeled with details which uniquely identify the product including: date of manufacture; date of expiration; lot number; reference number; and manufacturer information. Labels are affixed to outer foil packaging. The label should be retained for the subject's source records.

### **5.1.3 Product Storage and Stability**

The packaged BTM can be stored vertically or flat on a shelf in a secure location. There are no special storage requirements (e.g. temperature) although perforation of the packaging during storage or transport should be avoided as this will void sterility if penetration of the inner packaging occurs. The shelf life of the device is three (3) years. The device should not be used if the inner packaging has been opened, or obviously tampered with. If the inner packaging is found to be open, report and send the package as found back to PolyNovo.

## **5.2 Preparation and Administration of Investigational Device**

The sole investigational device in this traditional feasibility trial is the BTM. It is supplied with the seal factory-fenestrated and in pieces 20 cm x 40 cm. These can either be cut to size (for smaller wounds) or joined side-to-side (not overlapped) by stapling at seams (in large wounds). No special preparation of the BTM is necessary. It is removed from the outer packaging using sterile technique and opened from one end of the inner packaging to preserve the operating field. Full instructions are available in the Site Manual of Operations. Once opened, the BTM must be used or discarded and cannot be re-stored.

The BTM device is not intended to be used on the hands, face, neck, plantar skin, or perineal area. See Section 1.4.3 for detailed precautions.

Previous clinical use of BTM has demonstrated that integration rate of BTM and primary skin graft 'take' is decreased when BTM is used over bony prominences (such as the olecranon, spine of scapula, calcaneus), as pressure may inhibit integration. Standard pressure area precautions should be taken to ensure successful integration of BTM. In previous clinical use, BTM has been delaminated between Days 21 and 56 after implantation and this range will serve as a guide for this study. The timing of the de-

lamination is at the discretion of the Investigator based on his/her clinical and surgical judgement and could extend beyond 56 days if required.

### **5.3 Modification of Investigational Device for a Participant**

The number of BTM devices required by an individual subject depends on the size of the excised burn wound (between 10 and 70% of the total body surface area). In this traditional feasibility trial, subjects with deep partial or full thickness burns will have BTM devices implanted on at least 5% and a maximum of 50% of their TBSA of the sustained burns to be treated. This maximum is based on clinical experience to date treating burn areas with BTM (1% to 63% TBSA) (unpublished data of ongoing subjects).

### **5.4 Accountability Procedures for the Investigational Device**

PolyNovo's designee, PPD, will distribute, track and account for all investigational devices. Instructions for the investigational device return and/or destruction will be provided in the Site Manual of Operations.

